APPENDIX 3: Rosenberg Self-Esteem Scale	

GLOSSARY OF ABBREVIATIONS

CFR	U. S. Code of Federal Regulations
CRF	Case Report Form
DHHS	Department of Health and Human Services
GCP	Good Clinical Practices
HIPAA	Health Insurance Portability and Accountability Act
ICF	Informed Consent Form
ICH	International Conference on Harmonization
IRB	Independent Review Board
PP	Per protocol
WHO ^{odd}	World Health Organization Drug Dictionary

PROTOCOL SYNOPSIS

Title	The Emotional and functional benefits of Poly-L-Lactic Acid
Study Objective	To assess the emotional and functional benefits of Poly-L-Lactic Acid injections in the face
Study Population	Male and female subjects ≥ 35 years of age.
Study Design	Cross-sectional, multicenter trial.
Number of Sites	2 sites.
Total Number of Subjects	50 subjects.
Duration of Study	6 months.
Inclusion Criteria	
 1. Subject must be an outpatient, male or female subjects of any race, 35 years of age or older. 2. Subjects must have no evidence of clinically moderate to severe active acne activity or significant infectious process in the 6 months prior to study initiation. 3. Subjects of all Fitzpatrick skin types are eligible. 4. Subject must be able to follow study instructions and likely to complete all required visits, as assessed by the Investigator. 5. Subject must sign an IRB-approved Informed Consent form, Photographic Release Form, and the Authorization for Use and release of Health and Research Study Information (HIPAA) form prior to any study-related procedures being performed.
Exclusion Criteria	
 1. Any of the previous facial treatments: 
 a. Any facial filler in the past 2 years b. Prior injection of permanent facial implant 2. Have any skin pathology or condition that could interfere with the evaluation of the face. 3. Be unable to communicate or cooperate with the Investigator due to a language barrier (non-English speaking), poor mental development, or impaired cerebral function. 4. Have evidence of alcohol or drug abuse (Investigator opinion), or history of poor cooperation, non-compliance with medical treatment, or unreliability. 5. Have used an investigation device, biologic or drug in the past 30 days, or be currently participating in an experimental drug, biologic or device trial. 6. Have a condition or be in a situation that, in the Investigator's opinion, may put the subject at significant risk, may confound the study results, or may interfere significantly with the subject's participation in the study. 7. Be an employee (or a relative of an employee) of the Investigator, Sponsor or representative of the Sponsor.
Study Measurements	Subject self-reported quality of life scale
Study Procedures and Assessment Schedule	Eligible subjects will be given a self report questionnaire to complete 1 month after their second or third injection while in the physician's office. A subset of subjects will have baseline and post injection photographs taken.
Statistical Methods	Data will be summarized using descriptive statistics.

1. Background and Rationale

Facial volume loss can substantially impact both self perception of the affected individual and their social/professional interactions and opportunities. Persons who are perceived as more youthful and attractive are rated as nicer, more energetic, healthier, and more likely to be productive than those perceived to be older and unattractive.

The observed facial changes that result from underlying volume loss often produce an older and less attractive appearance. Loss of facial volume often produces a sad, sunken, deflated, dull, tired, and lackluster appearance. These changes can be interpreted as evidence of aging and loss. In addition, some may consciously or subconsciously see them as harbingers of progressive deterioration and decline. Filler correction of localized areas of facial volume loss has been demonstrated to affect positive changes in emotional and functional status by patient self report measures.

2. Current Clinical Study

A concern among some clinicians is the “delayed gratification” aspect of poly L-Lactic Acid. While its efficacy, safety, and duration of benefit are well supported by the literature, it is unique as a biostimulator leading to the gradual onset of tissue augmentation over several months. Many clinicians wonder whether patients will objectively “remember” their baseline appearance and thus be satisfied with their ultimate cosmetic outcome.

The goal of this study is to assess both the short term and longer term (3 months post first injection and 6 months post first injection) satisfaction with facial volume restoration with poly L-Lactic Acid.

Specifically, a patient self report questionnaire, previously utilized in several facial filler studies, will be completed by study participants at 3 months and six months after their initial facial injections to assess the emotional and functional effects produced by pan facial treatment with Poly-L-Lactic Acid. The obtained data will hopefully further enhance our appreciation and understanding of the benefits of facial volume restoration. Insight will hopefully be provided into the benefits of gradual onset of volumization with prolonged duration of improvement.

Buttressing and clarifying the data on the emotional and functional benefits of facial volume restoration can further “legitimize” treatment with poly L-Lactic Acid as an effective and meaningful medical procedure. Dissemination of data substantiating that volume restoration is more than simply a vanity or cosmetic intervention can serve as a compelling “recruitment tool” for the growing number of “maturing persons” struggling with the deflation and lackluster appearance that accompany the volume loss associated with aging, medications, stress, and illness.

3. Objectives

Objective 1: To assess the emotional and functional improvement produced by pan facial improvement with Poly-L-Lactic Acid

Objective 2: To assess to stability of these affects after treatment

Objective 3: To further substantiate the legitimacy and value of facial volume restoration.

4. Study Design

This is a multi-center study utilizing 2 centers (Yardley Dermatology Associates, [name] and Spokane Dermatology-[name] Aesthetics, [name]. Subjects will be recruited from private practice dermatology offices. Eligible patients must meet the inclusion and exclusion criteria as stated below.

5. Study Population

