5.1 Number of Subjects

50 male and/or female subjects 35 years of age or older who meet the protocol's participant eligibility requirements will be enrolled in the study at 2 investigational sites.

Study sites will be selected on the basis of experience in facial volume restoration and anticipated subject enrollment rate, with the objective of completing enrollment within approximately 2 months.

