8.3 Photography

Photographs for the study may be taken only at an investigators site as designated by the sponsor. Written training regarding study related photography will be provided during site initiation visits (where applicable).

9. Schedule of Study Activities

Subjects must meet all screening criteria as assessed by subject interview and through examination of facial volume loss. Please refer to the following schedule for additional details:

1. Discuss with each subject his/her willingness to participate in the study and obtain Informed Consent/HIPAA.
2. Inclusion/Exclusion Criteria
3. Document Subject Demographic Information
4. Subject Photography
 - a. To be conducted at baseline prior to first injection and 3 month and 6 month post initial injection. Photography instructions to be provided in a separate study document.
5. Facial volume loss assessment by Investigator and subject
 - a. Investigator/Subject Facial Volume Loss Global Assessment
6. Subjects will receive 1 vial of poly-L-lactic acid reconstituted in the usual sterile fashion with 7cc of sterile water and 2cc of Lidocaine without epinephrine. The contents of the vial will be injected as deemed appropriate by the certified injector and agreed upon by the study subject.
7. Approximately 4-6 weeks later, a second vial will be reconstituted as above and injected according to the above parameters.
8. Approximately 4-6 weeks later (8-12 weeks after the first injections), subjects will be evaluated and a decision jointly made with the injector regarding whether a third vial is desired and appropriate.
9. Injection sites will be prepared in the usual sterile fashion and sites will have Lidocaine topical application 30-90 minutes before the procedure.
10. All subjects will receive full informed consent and will have time for any questions before procedures are initiated.
11. Explicit post procedure instructions will be provided as per usual protocol.
12. Subjects will be instructed to contact the study site immediately with any concerns after each injection session.
13. QOL and Self-Esteem measures by subject
 - a. To be completed 3months and 6 months post initial injection.

10. Early Discontinuation/Withdrawal

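### Objective 1 credits emotional and functional improvement to Poly-L-Lactic Acid, but an uncontrolled design with no pre-treatment score can only describe change that subjects report after treatment

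*Combined protocol and SAP*

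**What the plan says.** **Aim.** Section 3 gives "Objective 1: To assess the emotional and functional improvement produced by pan facial improvement with Poly-L-Lactic Acid". Section 2 says that the questionnaire is to "assess the emotional and functional effects produced by pan facial treatment with Poly-L-Lactic Acid". The title and the synopsis objective speak of benefits, Objective 2 asks whether these effects are stable, and the third objective is "Objective 3: To further substantiate the legitimacy and value of facial volume restoration".

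**Design.** The synopsis calls the study a "Cross-sectional, multicenter trial". Section 5.1 states that "50 male and/or female subjects 35 years of age or older who meet the protocol's participant eligibility requirements will be enrolled" at two sites. Section 9 item 6 states that "Subjects will receive 1 vial of poly-L-lactic acid reconstituted in the usual sterile fashion", and item 7 gives everyone a second vial. No comparator, randomisation or masking is described anywhere.

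**Measures.** Section 9 item 13 schedules the quality-of-life and self-esteem measures at 3 and 6 months after the first injection. The synopsis gives a different time for the questionnaire, one month after the second or third injection. The two need reconciling, but both fall after treatment. Appendix 1 asks how subjects are since their injections, with 4 on a 1–7 scale meaning no change. Appendix 3, the Rosenberg scale, asks about the present. Photographs have a baseline (Section 9 item 4). The volume-loss grade (item 5) has no stated timing.

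**Analysis.** The synopsis says "Data will be summarized using descriptive statistics", and Section 13 says the same in substance. Neither places a limit on interpretation.

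**The concern.** The objective asks a causal question and the design supplies descriptive data. Every subject knows which product was injected, and the questionnaire stem invites the subject to link any change to it. Whatever expectation, imperfect recall, answering habit or unrelated life events add to the ratings goes into the score in full, and there is no group in which to see it separately.

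Recall is a doubt that the protocol raises itself: Section 2 notes that clinicians question whether patients remember how they looked at the start. The main instrument nevertheless depends on subjects comparing themselves with a remembered starting point.

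At stake is what the study may be said to have shown. Section 2 hopes that the data will help establish the treatment as an effective medical procedure and help attract patients, and Objective 3 points the same way. Perfect data and full compliance would still not support a statement that the product caused the improvement.

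**Working it through.** The plan gives no test, SD, effect size, power or interval, so there is no figure of its own to reproduce. The check is mainly a comparison of what the aim needs with what the schedule supplies.

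**1. What each measure can show**

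| Measure | Pre-treatment value? | Concerns emotion or function? | What it yields |
|---|---|---|---|
| Appendix 1, 35 items | No | Yes | Recalled change, product named |
| Rosenberg, Appendix 3 | No | Yes | Level after treatment |
| Photographs | Yes | No | Change in appearance |
| Volume-loss grade | Timing not stated | No | Appearance |

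No row has both a pre-treatment value and emotional or functional content, and no row has an untreated comparison.

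**2. What the mean estimates**

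Let τ be the true treatment effect and b the non-specific shift, both counted in the favourable direction from 4. The mean favourable shift estimates τ + b. There is one equation and two unknowns. As n grows, the standard error shrinks, but the estimate settles on τ + b, not on τ.

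**3. How small a shift could look like change (illustration)**

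Inputs: n = 50 (Section 5.1), all assumed evaluable; neutral value 4 (Appendix 1); SD assumed, since none is given.

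Half-width of a 95% interval = t(0.975, 49) × SD / √50, with t = 2.01 and √50 = 7.071:

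- SD 0.75: 2.01 × 0.75 / 7.071 = 0.21
- SD 1.0: 2.01 × 1.0 / 7.071 = 0.28
- SD 1.5: 2.01 × 1.5 / 7.071 = 0.43

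An observed mean further from 4 than this would give an interval that excludes no change.

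**4. The same point as a probability**

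Set τ = 0 and assume b = 0.5. By normal approximation, the chance that the interval excludes 4 on the favourable side is Φ(b / (SD/√50) − 1.96):

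- SD 1.0: Φ(3.54 − 1.96) = Φ(1.58) = 94%
- SD 1.5: Φ(2.36 − 1.96) = Φ(0.40) = 65%
- SD 2.0: Φ(1.77 − 1.96) = Φ(−0.19) = 42%

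Both b and the SD are assumptions. The documents give no means of estimating either.

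**5. Response style**

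Counting Appendix 1, 33 of 35 items put the favourable answer on the left. The exceptions are items 23 (medications) and 32 (alcohol). A habit of circling low numbers would therefore look like improvement on nearly every item.

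**The case against.** The strongest reply is that the plan is descriptive. It has no hypothesis test, success threshold or reporting rule. The objectives say that effects will be assessed, not that they exist, and much of Section 2 is expressed as hope. An uncontrolled survey is a legitimate study, and its limits are well understood.

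Much of this stands, and it rules out three stronger readings:

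- A reader might infer that any mean below 4 will be reported as improvement caused by the product. The documents contain no such rule and define no total or mean score. For items 23 and 32, a mean below 4 would point the unfavourable way.
- A reader might infer that only recalled change ratings are collected. That is too broad. The Rosenberg scale records current state, and photographs have a baseline. The accurate statement is that no emotional or functional measure has a pre-treatment score.
- A reader might take 0.28 point as the size of the bias. It is the precision of an interval that the plan does not compute, under an assumed SD.

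The reply does not remove the mismatch. Descriptive statistics do not make a causal objective descriptive, and nothing in the protocol tells the eventual author to stop at description. It is fair to add that the documents offer no evidence that expectation or response style will be large; the point is that the design could not tell.

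**Conclusion.** The concern holds as a mismatch between the stated aim and the design. Objective 1 and Section 2 attribute improvement to the product outright; the synopsis objective and Objectives 2 and 3 do so by implication. The data can support a description of change that subjects report after treatment, and the 3- and 6-month scores can describe its course. They cannot support attribution.

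This rests on reading the study as one open arm. The documents do not use those words, but treatment of every subject and the absence of any described control or masking leave no other reading.

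The bias has no size that can be derived from the documents. The half-width of about 0.28 point (0.21 to 0.43 for assumed SDs of 0.75 to 1.5, with 50 evaluable subjects) shows only that a modest non-specific shift could be mistaken for change. The documents do not support saying that a false conclusion is already planned. The change should be made because it governs what the study may conclude and is nearly free.

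**What to change.** 1. Restate Objective 1, the corresponding sentence in Section 2 and the synopsis objective as: *to describe the emotional and functional change that subjects report after facial treatment with Poly-L-Lactic Acid*.
2. Align Objective 2 (the course of reported change from 3 to 6 months) and Objective 3 with that wording.
3. In Section 13, state that Appendix 1 items are summarised at 3 and 6 months with a 95% confidence interval relative to the no-change value 4, and that items 23 and 32 are reverse-scored (8 minus the circled value) in any combined score.
4. State that Rosenberg scores are summarised separately as post-treatment levels. They must not be compared with 4, which on that scale is a response category (strong disagreement), not a neutral point.
5. State that the results are uncontrolled self-report and will not be reported as an effect of treatment.

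No control arm is requested. A baseline Rosenberg score would allow within-subject change to be described, but it would still not permit attribution and so would not replace the rewording.

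The cost is protocol text and a short addition to the analysis section, with no new visits, subjects or procedures. The downside is a weaker claim for the sponsor.

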5.1 Number of Subjects

50 male and/or female subjects 35 years of age or older who meet the protocol's participant eligibility requirements will be enrolled in the study at 2 investigational sites.

Study sites will be selected on the basis of experience in facial volume restoration and anticipated subject enrollment rate, with the objective of completing enrollment within approximately 2 months.

5.2 Inclusion Criteria

1. Subject must be an outpatient, male or female subjects of any race, 35 years of age or older.
2. Subject must have any degree of facial volume loss.
3. Subjects of all Fitzpatrick skin types are eligible.
4. Subject must be able to follow study instructions and likely to complete all required visits, as assessed by the Investigator.
5. Subject must sign an IRB-approved Informed Consent form, Photographic Release Form, and the Authorization for Use and release of Health and Research Study Information (HIPAA) form prior to any study-related procedures being performed.

5.3 Exclusion Criteria

1. Any of the previous facial treatments:
 - c. Any facial filler in the past 2 years
 - d. Prior injection of permanent facial implant
2. Have any skin pathology or condition that could interfere with the evaluation of the face.
3. Be unable to communicate or cooperate with the Investigator due to a language barrier (non-English speaking), poor mental development, or impaired cerebral function.
4. Have evidence of alcohol or drug abuse (Investigator opinion), or history of poor cooperation, non-compliance with medical treatment, or unreliability.
5. Have used an investigational device, biologic or drug in the past 30 days, or be currently participating in an experimental drug, biologic or device trial.
6. Have a condition or be in a situation that, in the Investigator's opinion, may put the subject at significant risk, may confound the study results, or may interfere significantly with the subject's participation in the study.
7. Be an employee (or a relative of an employee) of the Investigator, Sponsor or representative of the Sponsor.

6. Enrollment

Subjects will have the study explained and will be asked about their willingness to participate, including their willingness to sign an informed consent and a photography release form. To comply with Health Insurance Portability and Accountability Act (HIPAA) requirements, a separate authorization for disclosure or use of protected health information will be signed. After full consent, subjects will be considered enrolled into the study.

7. Informed Consent and Subject Privacy

The purpose and procedures to study participation will be discussed with each potential subject. Prior to any study-related procedures subjects must give their written informed consent. The subject must also give Authorization for Use and Release of Health and Research Study Information (HIPAA), authorization to take identifying clinical photographs for scientific and regulatory use and other written documentation required by local regulations and/or the reviewing IRB prior to any study-related procedures.

8. Study Assessments

Prior to enrollment of any study subjects, the Investigators will be trained in the use of the assessment scale. Subjects will receive training on how to complete the Volume Restoration Quality of Life Scale..

The Sponsor will prepare written procedures on how to perform digital imaging in a standardized fashion.

8.1 Investigator Global Assessment (IGA) of Facial Volume Loss

Grade	Description
0	No visible volume loss
1	Mild volume loss.
2	Moderate volume loss
3	Severe volume loss
4	Very severe volume loss

8.2 Subject Self- Report Quality of Life Instrument

A subject self-report instrument with 35 questions will be distributed to the subject for completion at the study site. This questionnaire is designed to assess the emotional and functional impact of facial acne scarring.

8.3 Photography

Photographs for the study may be taken only at an investigators site as designated by the sponsor. Written training regarding study related photography will be provided during site initiation visits (where applicable).

9. Schedule of Study Activities

Subjects must meet all screening criteria as assessed by subject interview and through examination of facial volume loss. Please refer to the following schedule for additional details:

1. Discuss with each subject his/her willingness to participate in the study and obtain Informed Consent/HIPAA.
2. Inclusion/Exclusion Criteria
3. Document Subject Demographic Information
4. Subject Photography
 - a. To be conducted at baseline prior to first injection and 3 month and 6 month post initial injection. Photography instructions to be provided in a separate study document.
5. Facial volume loss assessment by Investigator and subject
 - a. Investigator/Subject Facial Volume Loss Global Assessment
6. Subjects will receive 1 vial of poly-L-lactic acid reconstituted in the usual sterile fashion with 7cc of sterile water and 2cc of Lidocaine without epinephrine. The contents of the vial will be injected as deemed appropriate by the certified injector and agreed upon by the study subject.
7. Approximately 4-6 weeks later, a second vial will be reconstituted as above and injected according to the above parameters.
8. Approximately 4-6 weeks later (8-12 weeks after the first injections), subjects will be evaluated and a decision jointly made with the injector regarding whether a third vial is desired and appropriate.
9. Injection sites will be prepared in the usual sterile fashion and sites will have Lidocaine topical application 30-90 minutes before the procedure.
10. All subjects will receive full informed consent and will have time for any questions before procedures are initiated.
11. Explicit post procedure instructions will be provided as per usual protocol.
12. Subjects will be instructed to contact the study site immediately with any concerns after each injection session.
13. QOL and Self-Esteem measures by subject
 - a. To be completed 3months and 6 months post initial injection.

10. Early Discontinuation/Withdrawal

It is the right and duty of the Investigator to discontinue a subject's participation when the subject's health or well-being is threatened by continuation in the study. Such subjects should be withdrawn from the study. In the event of premature discontinuation, the Investigator should determine the primary reason for discontinuation. Subjects may voluntarily withdraw from the study at any time without jeopardy to future medical care. For any subject who withdraws from the study the date and reason for withdrawal will be recorded on the CRF.

11. Compliance with Protocol

The Investigator is responsible for compliance with the protocol at the investigational site. A representative of the Sponsor will make contact with the Investigator and his/her research staff to obtain completed CRFs.

12. Study Termination

If conditions arise during the study that indicate that the study or an investigational site should be terminated, the Sponsor, Investigator, Monitor, IRB, and/or regulatory agencies will discuss the situation and take appropriate action after consultation.

Conditions warranting termination of the study or site include, but are not limited to:

- The decision on the part of the Sponsor to suspend or discontinue evaluation, or development of the study.
- Failure of the Investigator to comply with pertinent national or state regulations, IRB-imposed conditions, or protocol requirements;
- Submission of knowingly false information from the Investigator to the Sponsor, IRB, or any regulatory agency.

13. General Statistical Analysis Methods

Relevant subject information i.e. demographics, facial volume restoration questionnaire answers will be collected and analyzed. This data will be summarized using descriptive statistics.

14. Administrative Issues

This protocol will be conducted in accordance with the applicable U.S. Food and Drug Administration (FDA) regulations and guidelines and Good Clinical Practice (GCP), i.e., the International Conference on Harmonization (ICH) Guideline on Good Clinical Practice.

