APPENDIX 1: Facial Volume Restoration Outcome Questionnaire

Site # _____ Subject # _____

Date: _____

Treatment visit 1 date: _____

Sex: Female Male

Treatment visit 2 date: _____

Age: 35-45 45-60 60-75

Treatment visit 3 date: _____

City/Country of residence: _____

Number of Poly-L-Lactic Acid treatments: _____

Please circle the number that best describes how you feel. Circling the number one suggests that you believe that the description on the left hand column best describes how you feel. Circling the number 7 suggests that you believe that the description on the right hand column best describes how you feel. Circling number 4 suggests that you feel that there has been no change. Please be honest.

Since my Poly-L-Lactic Acid injection (s), I find that I am in general...

1. Less anxious	1 2 3 4 5 6 7	More anxious
2. More optimistic	1 2 3 4 5 6 7	Less Optimistic
3. More energetic	1 2 3 4 5 6 7	Less energetic
4. Eating more healthy food	1 2 3 4 5 6 7	Eating less healthy food
5. Happier	1 2 3 4 5 6 7	Sadder
6. Exercising more	1 2 3 4 5 6 7	Exercising less
7. Less irritable	1 2 3 4 5 6 7	More irritable
8. More amorous	1 2 3 4 5 6 7	Less amorous
9. More social	1 2 3 4 5 6 7	Less social
10. More productive	1 2 3 4 5 6 7	Less productive
11. More focused	1 2 3 4 5 6 7	Less focused
12. Less tired	1 2 3 4 5 6 7	More tired
13. Less angry	1 2 3 4 5 6 7	More angry
14. More confident	1 2 3 4 5 6 7	Less confident
15. More sexually confident	1 2 3 4 5 6 7	Less sexually confident
16. More assertive	1 2 3 4 5 6 7	Less assertive
17. Less argumentative	1 2 3 4 5 6 7	More argumentative
18. More comfortable with others	1 2 3 4 5 6 7	Less comfortable with others
19. More likely to go out	1 2 3 4 5 6 7	Less likely to go out
20. More involved in community activities	1 2 3 4 5 6 7	Less involved in community activities
21. Doing better at work/school	1 2 3 4 5 6 7	Doing worse at work/school
22. More in control	1 2 3 4 5 6 7	Less in control
23. Taking more medications	1 2 3 4 5 6 7	Taking less medications
24. Less depressed	1 2 3 4 5 6 7	More depressed
25. Seen by others as less stressed	1 2 3 4 5 6 7	Seen by others as more stressed
26. Feeling more attractive	1 2 3 4 5 6 7	Feeling less attractive

27. More relaxed	1 2 3 4 5 6 7	Less relaxed
28. Happier when looking in mirror	1 2 3 4 5 6 7	Less happy looking in mirror
29. Using less cosmetics to hide defects	1 2 3 4 5 6 7	Using more cosmetic to hide defects

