APPENDIX 3: Rosenberg Self-Esteem Scale

Rosenberg Self-Esteem Scale

Circle one response for each of the following ten items.

	Strongly		Strongly	
	Agree	Agree	Disagree	Disagree
1. I feel that I am a person of worth, at least on an equal basis with others.	1	2	3	4
2. I feel that I have a number of good qualities.	1	2	3	4
3. All in all, I am inclined to feel that I am a failure.	1	2	3	4
4. I am able to do things as well as most other people.	1	2	3	4
5. I feel I do not have much to be proud of.	1	2	3	4
6. I take a positive attitude toward myself.	1	2	3	4
7. On the whole, I am satisfied with myself.	1	2	3	4
8. I wish I could have more respect for myself.	1	2	3	4
9. I certainly feel useless at times.	1	2	3	4
10. At times, I think I am no good at all.	1	2	3	4

Source: Morris Rosenberg's "Self-Esteem Scale" from pp-325-327 of *Society and Adolescent Self-Identity* 1989 by Morris Rosenberg, Wesleyan University Press.

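### Self-esteem is measured only at 3 and 6 months after the first injection, so its change from before treatment cannot be estimated

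*Combined protocol and SAP*

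**What the plan says.** Section 9, item 13 covers the subject-completed quality-of-life and self-esteem measures and sets two time points: "To be completed 3months and 6 months post initial injection". Photography, item 4 of the same list, is set before the first injection as well as at 3 and 6 months.

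The only self-esteem instrument in the document is the Rosenberg scale in Appendix 3. It has ten statements coded from 1 (strongly agree) to 4 (strongly disagree). Item 1 reads "I feel that I am a person of worth, at least on an equal basis with others" and item 3 reads "All in all, I am inclined to feel that I am a failure". The appendix cites a published source but prints no scoring rule.

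The 35-item questionnaire in Appendix 1 works differently. It asks about change since the injections, and its instruction says "Circling number 4 suggests that you feel that there has been no change".

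Section 3 gives Objective 1 as "To assess the emotional and functional improvement produced by pan facial improvement with Poly-L-Lactic Acid" and Objective 2 as "To assess to stability of these affects after treatment". Section 13 says "Relevant subject information i.e. demographics, facial volume restoration questionnaire answers will be collected and analyzed", to be summarised descriptively. It does not mention the Rosenberg scale.

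**The concern.** A scale of present state shows change only when two states are compared. With scores at months 3 and 6 alone, a given Rosenberg mean is the same evidence whether self-esteem rose, stayed level or fell after treatment. The scale therefore cannot support or contradict the improvement that subjects report from memory on the 35-item form.

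That matters because the 35-item form is otherwise the only emotional or functional measure of improvement. The volume-loss grade and the photographs concern appearance. Section 2 itself reports that clinicians doubt whether patients accurately remember how they looked at the start. That doubt is about appearance rather than mood, but it shows why a measure that does not depend on recall is useful here. Once a subject has had the first injection, the missing score cannot be obtained.

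**Working it through.** **1. Is there a starting value anywhere?**

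| Source | Time frame | Pre-treatment value? |
|---|---|---|
| Section 9, item 13 (quality of life, self-esteem) | 3 and 6 months after first injection | No |
| Section 2 (questionnaire) | 3 and 6 months after first injection | No |
| Synopsis (questionnaire) | 1 month after second or third injection | No |
| Appendix 3 (Rosenberg) | Present state, no comparison with an earlier time | No |
| Appendix 1 (35 items) | Recalled change since injection | Not a Rosenberg score |
| Section 9, item 4 (photographs) | Before first injection, 3 and 6 months | Yes, but of appearance |

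The plan has no control group and no reference value for the scale.

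**2. What can be estimated?** Write Y0, Y3 and Y6 for the Rosenberg total before treatment, at month 3 and at month 6.

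- mean(Y6 − Y3) can be estimated and bears on Objective 2.
- mean(Y3 − Y0) and mean(Y6 − Y0) need Y0, which is collected in 0 of 50 subjects. A larger sample does not help.

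**3. Does the total have a defined meaning?** Items 1, 2, 4, 6 and 7 are positive; items 3, 5, 8, 9 and 10 are negative.

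- Summed as circled, highest self-esteem: 5×1 + 5×4 = 25.
- Summed as circled, lowest self-esteem: 5×4 + 5×1 = 25.
- With positive items scored as 5 minus the circled number, highest: 5×4 + 5×4 = 40.
- With the same reversal, lowest: 5×1 + 5×1 = 10.

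No passage prescribes the raw sum. The point is that a rule is needed and none is stated.

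**4. What would a baseline give?** The plan states no standard deviation (SD), correlation or dropout, so there is no figure of its own to reproduce. The values below are assumptions: SD 4 to 6 points, correlation r between baseline and follow-up 0.3 to 0.7, and 40 to 50 complete pairs.

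SD of the change = SD × √(2(1 − r)). The 95% confidence interval half-width = t(0.975, n − 1) × SD of the change / √n.

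Worked case, SD 5, r 0.5, n = 50: SD of the change = 5 × √1 = 5; half-width = 2.01 × 5 / 7.07 = 1.42 points.

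| SD, r | Half-width, 50 pairs | Half-width, 40 pairs |
|---|---|---|
| 4, 0.7 | 0.88 | 0.99 |
| 5, 0.5 | 1.42 | 1.60 |
| 6, 0.5 | 1.71 | 1.92 |
| 6, 0.3 | 2.02 | 2.27 |

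On the 10 to 40 range, one added form would therefore estimate the mean change to within about 0.9 to 2.3 points.

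**The case against.** The strongest reply is that the plan never sets out to estimate change in self-esteem. No objective names it, the synopsis lists only a quality-of-life scale under its measurements, and Section 13 does not analyse it. The synopsis also calls the design cross-sectional, which fits a score taken only after treatment. Objective 1 keeps its own 35-item form, and the Rosenberg scale still serves Objective 2 through the month 3 to month 6 change. No passage gives it the role of corroborating recalled change.

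Most of this is correct, and it limits the severity. It does not remove the point. Section 9 describes repeated measures over time, not a single cross-section, and Objective 1 asks about improvement. If the scale is meant only to describe level and stability after treatment, the document does not say so.

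Two narrower objections also stand. The missing scoring rule is a separate defect from the missing baseline, and the 25-against-25 result does not measure the harm from the latter. The precision figures describe the remedy and rest on assumed values. The size of the problem itself is simply that no subject has a starting score.

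**Conclusion.** The concern holds. As written, 0 of 50 subjects have a pre-treatment Rosenberg score, so change in self-esteem from before treatment is not estimable. This follows from the schedule and the wording of the scale and needs no numerical assumption. The scale retains a limited use: level at months 3 and 6, and the change between them, once a scoring rule is stated.

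This should be fixed before first injections, but it does not invalidate the study, because self-esteem is in no objective and Objective 1 has its own instrument. A baseline would permit an uncontrolled before-after comparison and nothing stronger.

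**What to change.** Add to Section 9, item 13:

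> The Rosenberg Self-Esteem Scale is also completed at baseline, after consent and before the first injection.

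Add to Section 13:

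> Rosenberg total: items 1, 2, 4, 6 and 7 are scored as 5 minus the circled number and items 3, 5, 8, 9 and 10 as circled (range 10 to 40, higher = higher self-esteem). Mean within-subject change from baseline to 3 months, baseline to 6 months, and 3 to 6 months is reported with its 95% confidence interval and the number of pairs. It is an uncontrolled before-after change and is not described as an effect produced by treatment.

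The same amendment should list the scale in Section 8, say how unanswered items are handled, and bring the synopsis (design label, questionnaire timing, measurements) into line with Section 9. The causal wording of Objective 1 should be reviewed against the last sentence above.

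If a baseline cannot be collected, Section 13 should say that the scale describes only the level at months 3 and 6 and the change between them, and that nothing will be claimed about improvement since before treatment.

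The cost is one ten-item form, a few minutes per subject, and a short amendment. No extra visit, staff or subjects are needed, because every subject already has a pre-injection contact: "Subjects must meet all screening criteria as assessed by subject interview and through examination of facial volume loss". Section 14.1.1 already requires consent before any questionnaire, so the form fits directly after it.
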